2.8. Methods

2.8.1. Drugs and Dosage

Upon enrollment in the study, the participant will be randomly assigned to the Low Dose or the Fully Active Dose condition. Condition assignment will be performed with a table of random numbers generated by the Institute for Statistics, University of Bern. All study investigators will remain blind to condition assignment. If there is an adverse event or other emergency requiring knowledge of participant's condition assignment, the blind may be broken for an individual participant.

Participants in the Low Dose condition are assigned to receive an initial dose of 25 mg MDMA followed 2.5 hours later by a supplemental dose of 12.5 mg MDMA. Participants assigned to the Fully Active dose condition will receive an initial dose of 125 mg followed 2.5 hours later by a supplemental dose of 62.5 mg MDMA. Eight of 12 subjects, or 66.6%, will be assigned to the Fully Active dose condition, and 4 of 12, or 33.3%, will be assigned to the Low Dose condition.

The two doses of MDMA chosen for the Low Dose condition have been selected on the basis of their ability to produce minimal but detectable subjective effects (Grob et al. unpublished; Harris et al. 2002) and thus serve as an active placebo. The cumulative dose of 37.5 mg MDMA is not expected to produce a significant reduction in anxiety or a significant increase in access to emotionally upsetting material, though this dose may produce slight alterations in consciousness, such as increased relaxation or tension (Harris et al. 2002). The initial 125 mg dose of MDMA selected for the Fully Active Dose condition was chosen on the basis of case reports of MDMA-assisted psychotherapy conducted in the US prior to scheduling (Greer and Tolbert 1986), as well as on data obtained from [name] MAPS-sponsored MDMA/PTSD pilot study currently underway in the United States. This dose is expected to reduce fear in response to emotionally upsetting thoughts, feelings or memories and to increase access to emotionally intense material, and is thus expected to be therapeutically active. Doses equal to or exceeding 125 mg have been employed in previous uncontrolled and controlled studies of MDMA (Cami et al. 2000; Grob et al. 1996; Grob et al. Unpublished; Harris et al. 2002; Lester et al. 2000; Mas et al. 1999; Styk 2007; Tancer et al. 2001; Tancer et al. 2003; Vollenweider et al. 1998).

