2.8.6. Open Label Continuation for Active Placebo Patients ("Stage 2")

After each participant completes all outcome measures on the session scheduled 3 weeks after the third experimental session (T2), the participant will have a 30-minute meeting with the principal investigator. During this meeting, the blind will be broken for the individual participant while retaining the blind for the independent assessor. If a participant had received the Low (25 mg followed 2.5 hours later by 12.5 mg) dose of MDMA during the course of the study, she or he would be offered an opportunity to enroll in the open label continuation of the study, referred to as Stage 2. He or she would give written informed consent to take part in this second stage of the study, with consent given separately from the initial consent. If the participant consents to take part in Stage 2 of the study, he or she would receive the Fully Active dose of MDMA (125 mg followed 2.5 hours later by 62.5 mg) during three experimental sessions scheduled two to four weeks apart. Outcome measures administered three weeks after the third experimental session will serve as baseline measures for Stage 2. The participant would undergo one preparatory non-drug psychotherapy session 1 to 2 weeks prior to the first experimental session, and he or she would receive non-drug psychotherapy follow-up sessions according to the same schedule described for the active placebo controlled study. Procedures for non-drug psychotherapy sessions, experimental sessions, weekly telephone contact and outcome measure administration will be the same as those employed in the first stage of the study.

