The subject will be required to give written informed consent to take part in Stage 3 of the study, with consent given separately from the initial consent. If the participant consents to take part in Stage 3 of the study, he or she would receive an initial dose of MDMA that will either be identical to that used in Stage 1 and 2 or that of 150 mg, followed by a supplemental dose of up to 75 mg 2.5 hours later, during two experimental sessions scheduled two to four weeks apart. The investigators will use clinical judgment as the basis for determining initial and supplemental dose for each of the two Stage 3 sessions, and they may use their judgment to employ a different dose during the second session on the basis of their experience during the first Stage 3 session. Outcome measures administered 2 months (T3) after the third experimental session will serve as baseline measures for Stage 3. The participant would undergo one preparatory non-drug psychotherapy session 1 to 2 weeks prior to the first experimental session, and he or she would receive non-drug psychotherapy follow-up sessions according to the same schedule described for stage 1 of the controlled study. Procedures for non-drug psychotherapy sessions, experimental sessions, weekly telephone contact and outcome measure administration will be the same as those employed in the first stage of the study.

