4.0 Study design

The study followed a randomized, active placebo-controlled, double-blind design, with subjects, psychotherapists and independent raters blinded to participant condition. Twelve subjects with treatment-resistant PTSD were randomly assigned after baseline assessment to receive either full dose of 125 mg MDMA followed by a supplemental dose of 62.5 mg MDMA administered 2.5 h

later, or to an active placebo dose of 25 mg MDMA followed by 12.5mg MDMA 2.5h later. Participants underwent three sessions of MDMA-assisted psychotherapy scheduled to occur three to five weeks apart, 1 non-drug-psychotherapy session 24 h after each MDMA-session and 2-4 weekly integrative psychotherapy sessions after each MDMA session. PTSD symptoms were assessed by an independent rater once prior to MDMA-assisted psychotherapy, three weeks after the second MDMA-assisted session, three weeks after the third experimental session. After unblinding, active placebo participants had the opportunity to take part in an open-label continuation of the study, referred to here as "Stage 2." Data gathered three weeks after the third experimental session was treated as the baseline for Stage 2, and outcome measures were administered three weeks after the second and third experimental session. Originally outcome measures would also be given two, six and twelve months after the third experimental session, but the six-month evaluations were discontinued after January 2009 in line with the Amendment 5 of the protocol. Participants receiving the full dose in either Stage 1 or Stage 2 who did not show significant improvement in PTSD symptoms were offered the opportunity to take part in an open-label continuation of the study, "Stage 3", consisting of two additional MDMA sessions. During these sessions, they could receive 125 mg followed 2.5 hours later by 62.5 mg MDMA or a 20% larger dose of 150 mg MDMA, followed by a supplemental dose of 75 mg administered 2.5 hours later, unless contraindicated by safety parameters. Outcome measurements gathered at 2 months after the third experimental session will serve as baseline measures for Stage 3. Stage 3 was also cancelled in line with Amendment 5. Of the 12 participants who completed the study, only three participants underwent Stage 3.

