6.5.1 Main Analysis

Physiological Measures and SUD

Analysis #1

Goal: to test the presence of a main effect of condition (125 mg MDMA, 25 mg MDMA, 150 mg MDMA in Extended Assessment 2) on changes in vital signs and psychological distress,

Population: All enrolled, intention to treat, per protocol, partial crossover, Extended Assessment 2

Data included: Pre-drug average, maximum change (peak) and post-drug average SBP, DBP, HR, BT and SUD, number of participants with vital signs above clinical cut off and duration above clinical cut-off

Format of Analyses: One-way ANOVA per each experimental session, including sessions during Stage 1, Stage 2 and Stage 3

Between-Group Factor: Condition (125 mg MDMA, 25 mg MDMA, 150 mg MDMA in Extended Assessment 2)

Analysis #2

Goal: To test effects of condition, presence or absence of supplemental dose and time of session on physiological data and psychological distress during experimental sessions

Population: All enrolled, intention to treat, per protocol

Data included: Pre-drug average, maximum change (peak) and post-drug average SBP, DBP, HR, BT and SUD, number of participants with vital signs above clinical cut off.

Format of analysis: Repeated measures ANOVA

Time: Session (Experimental 1, Experimental 2, Experimental 3)

Between Groups Factors: Condition (125 mg MDMA, 25 mg MDMA) as between-group factor, and supplemental dose (given, not given) as second between-group factor.

Analysis #3

Goal: To test effects of condition, presence or absence of supplemental dose and time of session on physiological data and psychological distress during Stage 2 or Stage 3 sessions.

Population: Partial crossover, Extended Assessment 2

Data included: Pre-drug average, maximum change and post-drug average SBP, DBP, HR, BT and SUD, number of participants with vital signs above clinical cut off, and duration above clinical cut-off.

Format of analysis: Repeated measures ANOVA

Time: Crossover Session (Stage 2 Experimental Session 1, 2, and 3, Stage 3 Experimental sessions 1 and 2)

Between-Subjects factors: Supplement (present, absent)

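### The SAP's main vital-sign and distress analysis can be estimated only for 125 v 25 mg in Stage 1; it cannot usefully test 150 mg, and no analysis sets 150 mg, by dose, against a participant's own 125 mg sessions

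*SAP*

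**What the plan says.** SAP 6.5.1 Analysis #1 covers pre-drug, peak and post-drug blood pressure, heart rate, temperature and SUD, plus counts and durations above the clinical cut-off. The method is "Format of Analyses: One-way ANOVA per each experimental session, including sessions during Stage 1, Stage 2 and Stage 3". The factor is "Between-Group Factor: Condition (125 mg MDMA, 25 mg MDMA, 150 mg MDMA in Extended Assessment 2").

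The doses that each stage can contain are fixed elsewhere:

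- **Stage 1** (Protocol 2.8.1): "Eight of 12 subjects, or 66.6%, will be assigned to the Fully Active dose condition", and the other four to the low dose.
- **Stage 2** (Protocol 2.8.6), for former low-dose participants: "he or she would receive the Fully Active dose of MDMA (125 mg followed 2.5 hours later by 62.5 mg) during three experimental sessions".
- **Stage 3** (SAP 4.0): "they could receive 125 mg followed 2.5 hours later by 62.5 mg MDMA or a 20% larger dose of 150 mg MDMA". Protocol 2.8.7 adds that "The investigators will use clinical judgment as the basis for determining initial and supplemental dose for each of the two Stage 3 sessions", and that "they may use their judgment to employ a different dose during the second session".
- **Numbers in Stage 3** (SAP 4.0): "Of the 12 participants who completed the study, only three participants underwent Stage 3".

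Two other parts of the SAP bear on the higher dose. Analysis #3 in 6.5.1 is a repeated-measures ANOVA of the same measures over Stage 2 sessions 1 to 3 and Stage 3 sessions 1 and 2. Its goal names condition, but its only between-subject factor is whether the supplement was given. The adverse-event analyses in 6.5.3 test number and severity by dose, including 150, 212.5 and 225 mg, with dose again as a between-group factor.

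**The concern.** A one-way ANOVA within a session needs at least two dose groups in that session and enough people to estimate error. The plan asks for this test in all three stages with a three-level factor, yet no session can contain all three doses. The part of the goal that concerns 150 mg depends on the two Stage 3 sessions, where three people received a dose chosen for them individually.

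The protocol itself expects 150 mg plus 75 mg to raise blood pressure and heart rate more than 125 mg does (4.2), and side effects to increase with the higher dose (2.8.1). Stage 3 is the trial's only source of data at 150 mg. Everyone who entered it had already been through the 125 mg regimen, under the same vital-sign schedule. The natural comparator is therefore already in the database, but no analysis uses it by dose. A test that returns no result, or cannot reject, could be read as reassurance.

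**Working it through.** The documents give no sample size, SD or power for 150 mg, so there is no stated figure to reproduce. The check has four steps.

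**1. Which doses meet in which session.** There are 3 + 3 + 2 = 8 session positions.

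| Stage | Sessions | Doses possible | People | Between-group df, error df |
|---|---|---|---|---|
| 1 | 3 | 25, 125 mg | 4 v 8 (planned) | 1, 10 |
| 2 | 3 | 125 mg | at most 4 under the planned allocation | 0: no test |
| 3 | 2 | 125, 150 mg | 3 | 1, 1 at best; 0 if all had one dose |

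Error df = people − groups: 12 − 2 = 10 in Stage 1 and 3 − 2 = 1 in Stage 3. Three positions are estimable as intended, three have no test, and two have at most one error degree of freedom.

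**2. What the Stage 3 test can detect.** Assumptions: alpha 0.05 two-sided, equal SDs, effect in between-person SD units. With a 2/1 split the critical F(1,1) is 161.4 (t = 12.71). Simulated power (200,000 runs) is 6.7%, 10.5% and 15.4% for differences of 1, 2 and 3 SD. Power reaches 80% only at about 20 SD.

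**3. What the within-person contrast offers.** Suppose all three received 150 mg in both Stage 3 sessions, and each person's mean of two 150 mg sessions is compared with the mean of three own 125 mg sessions. With correlation ρ between any two sessions:

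Variance of the mean difference = (1 − ρ)(1/2 + 1/3)/3 = (1 − ρ)(5/6)/3, with df = 2 and critical t = 4.30.

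| ρ (assumed) | Power at 1 SD | 2 SD | 3 SD | Detectable with 80% power |
|---|---|---|---|---|
| 0.3 | 26% | 65% | 90% | 2.5 SD |
| 0.5 | 33% | 77% | 96% | 2.1 SD |
| 0.7 | 47% | 91% | 99% | 1.6 SD |

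With one session at each dose, the detectable differences are 3.9, 3.3 and 2.5 SD. The paired contrast uses the data far better than the 2/1 comparison, but three people still do not support a formal test. If fewer than three received 150 mg, it is weaker again.

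**4. Whether other analyses fill the gap.**

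- *Analysis #3.* Someone who went from Stage 2 into Stage 3 has Stage 3 sessions set against their own 125 mg sessions. Dose is not in the model, so any dose difference appears only as a session difference. Someone who entered Stage 3 directly from the Stage 1 full-dose arm has no Stage 2 sessions, and their Stage 1 sessions are not in the time factor. If cases need all five sessions, there are 0 to 3 complete cases. Within-person error df, before the supplement factor, is 4(m − 1) = 0, 4 or 8 for m = 1, 2 or 3.
- *Adverse-event analyses.* These classify by dose but treat the dose groups as different people, and they do not cover vital signs or SUD.
- *Pooling by session number across stages.* The SAP does not state this, but it might be tried. It gives up to 12 + 4 + 3 = 19 records from 12 people and a nominal error df of 19 − 3 = 16. If all three Stage 3 participants are at 150 mg, the simulated true size of the nominal 5% test is 3.0–3.7% at ρ = 0.3 and 1.3–2.0% at ρ = 0.7. Independence fails and the test becomes conservative, which is unhelpful when looking for a safety signal.

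**The case against.** The strongest reply is that the plan is less bare than this suggests and that little depends on it. Much of that reply stands.

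- A reader might infer that the doses never meet. Only the three-way meeting is impossible: 25 and 125 mg meet in every Stage 1 session, and 125 and 150 mg can meet in Stage 3. The randomised part of Analysis #1 is sound in this respect.
- A reader might infer that the plan ignores participants' own 125 mg sessions. It does not, because Analysis #3 uses them for those who passed through Stage 2. What is missing is dose in that model and the Stage 1 sessions of direct entrants.
- A reader might infer that every Stage 3 session would be coded as 150 mg. The factor wording can equally mean a 150 mg level that occurs within that population, and SAP 6.5.3 classifies by amount given. The documents show no misclassification; Analysis #1 simply lacks a coding rule.
- A reader might infer that 150 mg gets no other safety analysis. Adverse events are tabulated and tested by dose.
- Individual listings of all clinical data are already promised (SAP 6.1), as are vital-sign summaries by condition and session (SAP 6.5). The paired difference adds a dose label and a subtraction.
- A test with one group yields nothing, and one with a critical F of 161.4 will rarely yield a false alarm. No randomised or primary result is affected.

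None of this makes the 150 mg part of Analysis #1 workable, or supplies a comparison of 150 with 125 mg within person by dose.

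**Conclusion.** The point holds, within limits. As written, Analysis #1 can meet its goal for 125 v 25 mg in three of eight session positions. It gives no test in three, and at best a 2 v 1 comparison with one error degree of freedom in two. It cannot usefully test 150 mg. Analysis #3 only partly compensates, and the adverse-event tests do not replace it.

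The finding about which doses can meet rests on the design alone. The power figures rest on assumed equal SDs, ρ of 0.3 to 0.7 and all three Stage 3 participants receiving 150 mg. The documents give neither the number given 150 mg (0 to 3) nor how many entered from Stage 1 or Stage 2. The 8 v 4 split is the planned allocation; the intention-to-treat set could differ if a drop-out was replaced.

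The consequence is modest: a main safety analysis that cannot deliver one of its stated comparisons, in three people. It does not show that a safety signal was missed, or that 150 mg differs from 125 mg.

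**What to change.** In SAP 6.5.1:

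1. Restrict the Analysis #1 ANOVA to the three Stage 1 sessions, 125 v 25 mg. Describe Stage 2 without a test; SAP 6.5.2 Analysis #2 already compares randomised with open-label full-dose sessions.
2. Classify each Stage 3 session by the dose actually given, recording initial dose and supplement separately.
3. For each participant given 150 mg, list the 150 mg session value(s) minus the mean of that person's own 125 mg sessions, from Stage 1 or Stage 2 as applicable. Do this for peak and post-drug SBP, DBP, HR, temperature and SUD. Show individual values without a p-value.
4. Add dose given, and the Stage 1 full-dose sessions of direct entrants, to Analysis #3, or make that analysis descriptive.
5. State the limits beside the listing: how many received 150 mg, and that the differences are confounded with session order, open-label status (for direct entrants) and selection of insufficient responders.

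The cost is SAP wording and one listing from data already collected. The only thing given up is the claim to a formal test of 150 mg, which the design could not support.

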6.5.2 Subsidiary analyses

Physiological and SUD:

Analysis #1

Goal: To test for the presence of interactions between demographic variables and condition on one or more physiological variable or psychological distress. Performed if and only if there are significant differences in representation of a given demographic variable or feature across conditions (as, more women in one condition than the other), or if doing so gathers essential information on study drug safety.

Population: All enrolled, intention to treat, per protocol, partial crossover

Data included in analyses: Peak SBP, DBP and HR, peak SUD

Format of Analysis: Two-way analysis of variance, one per experimental session in each stage

Between-group factors: Demographic variable (e.g. gender), Condition (125 mg MDMA, 25 mg MDMA).

Analysis #2

Goal: To determine if there is an effect for Stage (e.g. order of administration) upon measures of physiological response or psychological distress taken during full-dose MDMA sessions.

Population: Intention to treat, per protocol [125 MDMA only], partial crossover [previously assigned to 25 mg MDMA]

Data included in analyses: Pre-drug average, peak and post-drug average vital signs computed across all subjects averaged across 1) Randomized or 2) Open label full dose sessions

Format of analysis: Full repeated measures ANOVA

Between group factor: Blinding (Randomized, Open Label)

6.5.3 Adverse Events

Summary Tables

Goal: To present adverse events organized by drug dose, defined here as total amount of study drug per session near AE or reaction, including initial dose and supplement if administered, , seriousness, severity and relatedness to the study drug

Population: All enrolled, Intention to treat, Per protocol, Partial crossover, Extended Assessment 1, Extended Assessment 2

Categorical data includes: Number of AEs per subject; Number of severe AEs; Instances of occurrence of each spontaneously reported reactions by condition (MDMA, Placebo) and Stage (Stage 1, Stage 2); Adverse events (AE identity, seriousness (Yes/No), severity (mild, moderate, severe), onset, resolution, relatedness to study drug (not related, possibly related, probably related); Spontaneously reported reactions listed by MedDRA (Version 14) System Order Class

Format of presentation: This data will be presented in several summary tables of counts per subject, by drug dose, or across the course of the study, as appropriate for the data or descriptive statistics being listed.

Content of Presentation: Number of AEs per subject; Number of severe AEs; Instances of occurrence of each spontaneously reported reactions by condition (MDMA, Placebo) and Stage (Stage 1, Stage 2), number of severe spontaneously reported reactions;Adverse events (AE identity, seriousness (Yes/No), severity (mild, moderate, severe), onset, resolution, outcome, relatedness to study drug (not related, possibly related, probably related); Spontaneously reported reactions listed by MedDRA Version 14 System Order Class

Descriptive data includes: Overall number of AEs, severity of AEs, Peak Demeanor after each experimental and open label session, Overall number of spontaneously reported reactions, average reported severity of spontaneously reported reactions

Format of Presentation: Summary tables of frequency listings in total, by condition, by session, by subject and by condition

Content of Presentation: Adverse Event Listings (All possibly and probably related AEs, all AES occurring within seven days of drug administration, all severe AEs, and number of severe AEs by condition); AE or severity of AE and peak demeanor after each experimental or open label session by condition (MDMA, placebo, partial crossover).

Tabular Listing of Adverse Events

Goal: To follow guidance for display of adverse events

Population: All enrolled, intention to treat, per protocol, partial crossover, Extended Assessment 2

Data included: Per each AE; Subject number, Patient identifier

- Age, race, sex, weight (height, if relevant)
- Location of CRFs, if provided
- Adverse event description (preferred term, reported term)
- Duration of the adverse event
- Severity (e.g., mild, moderate, severe)
- Seriousness (serious/non-serious)
- Action taken (none, dose reduced, treatment stopped, specific treatment instituted etc.)
- Outcome (e.g., CIOMS format)
- Relatedness process of determination given if possible
- Date of onset or date of clinic visit at which the event was discovered
- Timing of onset of the adverse event in relation to last dose of investigational product (if or when applicable)
- Investigational product dose in absolute amount, mg/kg
- Duration of investigational product treatment (Stage 1, Stage 2, Stage 3)
- Concomitant treatment during study.

Format of presentation: All adverse events for each patient, including the same event on several occasions will be listed, giving both preferred term and the original term used by the investigator. The listing should be by treatment group and will include:

Analysis #1

Goal: To see if one or more demographic factor and condition alter the number and severity of adverse events and spontaneously reported reactions collected across the course of the study.

Population: All enrolled, intention to treat, per protocol, partial crossover, Extended assessment 1, Extended assessment 2

Data included: Number of AEs collected across Stage 1, Stage 2 and Stage 3, and any AEs collected before 2, 6 and 12 month follow up for Extended Assessment 1 participants, Number of severe AEs collected across Stage 1, Stage 2 and Stage 3 (when applicable), average severity rating of AEs occurring during the study, number of individual spontaneously reported reactions and average severity of self-reported reactions.

Format of analysis: Two-way ANOVA for gender, linear regression analysis for age

Between-groups factors: Condition (125 mg MDMA, 25 mg MDMA, 150 mg MDMA (when applicable)); gender; age

Analysis #2

Goal: to see if there is an effect of presence versus absence of supplemental dose upon number of AEs and spontaneously reported reactions and number of severe AEs and spontaneously reported reactions.

Population: All enrolled, intention to treat, per protocol, partial crossover, extended assessment 2

Data included: Number of AEs across all study stages, number of severe AEs across all study stages

Format of analysis: One-way ANOVA

Between groups factor: Dosage (25 mg MDMA, 37.5 mg MDMA, 125 mg, 187.5 mg, 150 mg MDMA, 212.5 mg MDMA, 225 mg MDMA)

Analysis #3

Goal: To see if demographic variables interact with dose of study drug; performed if and only if a previous analysis establishes that gender, age or presence of another affective disorder produce an interaction with condition.

Population: All enrolled, intention to treat, per protocol, partial crossover, Extended assessment 1, Extended assessment 2

Data included: Number of AEs across all study stages, number of severe AEs across all study stages.

Format of analysis: Two-way ANOVA for categorical data, regression analysis for continuous data

Between-group factors: Demographic factor (gender (male, female), age, presence of another affective disorder), study drug dose (25 mg, 37.5 mg, 125 mg, 187.5 mg, 150 mg, 212.5 mg, 225 mg MDMA)

